4 will be performed to permit retrospective determination of the characteristics of an effective product and
5 dosage regimen, and the characteristics of patients most likely to benefit¹⁸.

6 Data and blood specimen will be banked for future use pursuant to the IRB Approved Inova COVID-19
7 Biobanking Protocol. We will follow the guidelines and procedures for specimen storage and access as
8 described in the IRB approved Inova COVID-19 Biobanking Protocol.

9 Specimens will be stored at the Office of Research at Inova Biobank with standard certifications in place.

10

1 **PLASMA RECIPIENTS:**

2 **Inclusion Criteria for Recipients of COVID-19 Convalescent Plasma:**

3 Patients in the Inova Health System with confirmed COVID-19 by PCR testing

4 Age \geq 13 years

5 Currently hospitalized with COVID-19 infection with severe or life-threatening clinical syndrome²² as
6 follows:

7 Severe COVID-19: (three or more of the following)

8

- 10 • Dyspnea
- 11 • Respiratory rate \geq 30/min
- 12 • Blood oxygen saturation (SpO₂) \leq 94% on room air
- 13 • Partial pressure of arterial oxygen to fraction of inspired oxygen (P:F) ratio $<$ 300
- 14 • Pulmonary infiltrates $>$ 50% of lung parenchyma within 24 to 48 hours

15 Life-threatening disease is defined as: (one of the following)

- 16 • Respiratory failure
- 17 • Septic shock, and/or
- 18 • Multiple organ dysfunction or failure

19 Patient must provide informed consent or have health care power of attorney/next of kin provide consent
20 if he/she cannot.

21 **Exclusion Criteria:**

22 Contraindication to receive plasma as deemed by the treating physician

23 Severe hypercoagulable state (documented in medical chart or by treating physician assessment)

24 Absolute IgA deficiency

25 Prior history of Transfusion Related Acute Lung Injury (TRALI)

26 Inability to tolerate plasma volume due to severe systolic or diastolic heart failure despite slower infusion
27 and diuretic administration

28 Positive pregnancy test (HCG)

29 **Recipient Screening Labs**

30 Blood Type

31 Total immunoglobulin (Ig) levels: IgG, IgA, IgM

32 Coagulation tests to include PT/INR and PTT

33 Complete blood count and differential

34 **Pre-Treatment Testing:**

35 Optional Blood draw for Inova COVID-19 Biobank (up to four tubes each) prior to each dose of plasma

36 **Target Recipient Recruitment:** 150-200 individuals

37 **Primary Endpoints:**

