21 transformations explored as needed. All analyses will be conducted using SAS (version 9.4, Cary, NC)
22 with p<0.05, two-tailed considered statistically significant.

23
24 Primary efficacy endpoints:

25 1. Gilead 7-point scale – For each time point (day 0 vs. 7), summary clinical status scores will be
26 calculated. Changes in scores will be subsequently assessed via a generalized linear mixed model
27 with clinical status assessed at day 0 vs. 7. A statistically significant increase of ± 2 points in β
28 from day 0 to day 7 will be considered as evidence of efficacy. A mixed model allows for
29 examination and inclusion of the variance-covariance matrix into the model as a result of expected
30 within-subject serial correlation as a result of repeated assessments over time.
31 2. Plasma transfusion related adverse events will be scored as 1+ vs. 0 and will be assessed via Chi-
32 Square test with a hypothesized distribution of expected AE (using the higher incidence estimate):
33 i. Transfusion Associated Circulatory Overload: 1:1,566 to 1:68 plasma units
34 transfused
35 ii. Transfusion-Related Lung Injury: 1:1,200 to 1:190,000
36 iii. Allergic Reaction/Anaphylaxis: 1-3%
37 iv. Febrile Transfusion Non-hemolytic Transfusion Reaction: 0.1-1%

38
39 Secondary endpoints:

40 1. Change in 7-point ordinal scale score and SOFA score over time will be assessed via individual
41 growth models (IGM). Times will be day0, 14, 21, and 28
42 2. Mortality will be assessed via Chi-Square test with a hypothesized current mortality rate of 1-5%
43 (age adjusted).
44 3. Need for mechanical ventilation for those not ventilator at time of plasma infusion will be
45 assessed via Chi-Square test with a currently available published estimates.

1 4. Time to discontinuation of supplemental oxygen, time to liberation from mechanical ventilation,
2 duration of hospitalization will be summarized as median (IQR) or rates and compared to currently
3 available published estimates.
4
5

6 **ADVERSE EVENTS AND TOXICITY MANAGEMENT**

7 **Definitions of Adverse Events and Serious Adverse Events**

9 **Adverse Events (AE)**

10 An AE is any untoward medical occurrence in a clinical study subject administered an investigational
11 product, which does not necessarily have a causal relationship with the treatment. An AE can therefore be
12 any unfavorable and/or unintended sign, symptom, or disease temporally associated with the use of an

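### The chi-square test of transfusion reactions against the top of each published range is unreliable at 150–200 recipients, and a non-significant result cannot support a finding of no excess

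*Combined protocol and SAP*

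**What the plan says.** The Primary Endpoints section lists reactions within 6 hours of infusion as the second primary endpoint. Item 2 under Primary efficacy endpoints in the Statistical Plan reads "Plasma transfusion related adverse events will be scored as 1+ vs. 0 and will be assessed via Chi"-"Square test with a hypothesized distribution of expected AE (using the higher incidence estimate"). The reference ranges that follow are:

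- "Transfusion Associated Circulatory Overload: 1:1,566 to 1:68 plasma units" transfused
- "Transfusion-Related Lung Injury: 1:1,200 to 1:190,000"
- "Allergic Reaction/Anaphylaxis: 1-3" percent
- "Febrile Transfusion Non-hemolytic Transfusion Reaction: 0.1-1" percent

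The general rule for all analyses is "with p<0.05, two-tailed considered statistically significant". Target recipient recruitment is "150-200 individuals". The Dosing section allows one dose and up to two more.

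For this test the plan gives no direction, margin, interval, power or rule of interpretation. It does not say whether the 1+ versus 0 score is kept for each reaction type or for any reaction, or whether the unit is the patient or the plasma unit. Only circulatory overload has a stated denominator, which is units.

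**The concern.** The recipient part has no control group, so this comparison is its formal safety test. Three of the four reactions are rare against the planned sample size, and a chi-square approximation fails when expected counts are small. The reference is the top of ranges that span 23-fold (circulatory overload), 158-fold (lung injury), 3-fold (allergic) and 10-fold (febrile).

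A reader is likely to take a non-significant result as evidence that convalescent plasma caused no more reactions than expected. If the test could not have shown otherwise at this size, the conclusion is empty. In the other direction, one event of the rarest type could be reported as a significant excess merely because the approximation has broken down.

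**Working it through.** **Inputs.** Higher reference rates p0 (Statistical Plan, item 2): circulatory overload 1/68 = 1.47%; lung injury 1/1,200 = 0.083%; allergic 3%; febrile 1%. Low ends: 1/1,566 = 0.064%; 1/190,000 = 0.0005%; 1%; 0.1%. n = 150 and 200; two-sided 5% level, critical value 3.84. Assumption for steps 1–4: one observation per recipient. The plan gives no critical count or power for this test, so there is no figure to reproduce.

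**1. Expected counts, n × p0 (n=150 / 200).** Circulatory overload 2.2 / 2.9; lung injury 0.125 / 0.167; febrile 1.5 / 2.0; allergic 4.5 / 6.0.

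**2. One lung-injury event.** X² = (x − n·p0)² / [n·p0·(1 − p0)].
- n=150: (1 − 0.125)² / (0.125 × 0.9992) = 6.13, p = 0.013.
- n=200: (1 − 0.167)² / (0.167 × 0.9992) = 4.17, p = 0.041.
- Exact chance of at least one event at the reference rate: 1 − (1 − 1/1,200)^150 = 0.118; with exponent 200, 0.154.

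So a nominal 5% test raises a false alarm 12–15% of the time. A continuity correction reverses the result: X² = (0.875 − 0.5)²/0.125 = 1.13 (p = 0.29) at n=150, and 0.67 (p = 0.41) at n=200. The plan does not say which version is meant.

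**3. Smallest count flagged as an excess.**

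| Reaction | n=150 | n=200 |
|---|---|---|
| Circulatory overload | 6 (4.0%), X²=6.62 | 7 (3.5%), X²=5.68 |
| Allergic | 9 (6.0%), X²=4.64 | 11 (5.5%), X²=4.30 |
| Febrile | 4 (2.7%), X²=4.21 | 5 (2.5%), X²=4.55 |
| Lung injury | 1 (0.7%) | 1 (0.5%) |

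For febrile reactions the exact upper-tail probabilities at these counts are 0.065 and 0.052, against chi-square p-values of 0.040 and 0.033.

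**4. What zero events can exclude.** The Clopper-Pearson 95% upper limit at zero is 1 − 0.025^(1/n): 2.4% at n=150 and 1.8% at n=200. Both exceed the higher figures for circulatory overload (1.47%), febrile reactions (1%) and lung injury (0.083%). Only the allergic figure (3%) lies above them.

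**5. Can a rate above the low end be declared significantly lower?**
- *Each type, 150–200 recipients: no.* Zero events gives p = 0.135 / 0.084 (circulatory overload), 0.72 / 0.68 (lung injury) and 0.22 / 0.155 (febrile). Allergic needs 0/150 or at most 1/200 = 0.5%, below its 1% low end.
- *Any reaction, rates summed, one infusion each.* The higher sum is 1.47 + 0.083 + 3 + 1 = 5.55%; the low sum is 0.064 + 0.0005 + 1 + 0.1 = 1.16%. At n=150, 2 events give (2 − 8.33)²/(8.33 × 0.944) = 5.09, p = 0.024. At n=200, 4 events give (4 − 11.11)²/(11.11 × 0.944) = 4.82, p = 0.028. These rates, 1.33% and 2.0%, are 1.1 and 1.7 times the low sum. One more event is not significant in either case. At a true rate of twice the low sum (2.33%), a lower verdict has probability 0.32 (n=150) or 0.50 (n=200).
- *Per unit, 200 recipients × 3 doses = 600 units, treated as independent.* Circulatory overload: expected 600/68 = 8.82; 3 events give (3 − 8.82)²/(8.82 × 0.985) = 3.90, p = 0.048. The rate 3/600 = 0.50% is 7.8 times its low end (0.50/0.064).

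**The case against.** A reader might infer something stronger: that taking the top of each range as reference generally lets reaction rates well above the low end be declared significantly lower than expected. The documents do not support that. The plan lists four separate rates and no combined one. Tested type by type on 150–200 recipients, none can be declared lower at a rate above its own low end (step 5). The 5.55% sum appears nowhere in the plan and is built here. It also depends on one infusion each: if scoring is per patient and every recipient has two independent doses at twice the low-end risk, the probability of a lower verdict falls from 0.32 and 0.50 to 0.029 and 0.045. With three doses it is about 0.002. The plan makes no claim of a lower rate; a two-tailed test with no stated direction merely leaves room for one.

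The higher reference is also disclosed and may be defensible, since recipients have severe or life-threatening disease. The documents cannot settle which end suits them. Nor is the test permissive throughout, because one lung-injury event rejects. Formal tests against the low ends would have a cost: a true febrile rate of 1%, inside the published range, would be flagged against the 0.1% end with probability 0.44–0.60. Finally, the plan already reports frequencies and percentages, and weak power for rare events partly reflects sample size, which no analysis method cures.

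All of this stands, and it limits the point. It does not rescue the chi-square test at these expected counts, or make a non-significant result informative.

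**Conclusion.** The concern holds in a limited form. At 150–200 observations the planned test is unreliable for three of the four reactions, with expected counts between 0.125 and 2.9. It flags a single lung-injury event that has a 12–15% chance under the reference rate. It needs 3.5–4.0% circulatory overload, or 5.5–6.0% allergic reactions, before flagging an excess. A non-significant result cannot support a no-excess statement: for circulatory overload, lung injury and febrile reactions, not even zero events would do so.

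A significantly lower result at a rate above the low end arises only on some readings the plan leaves open: any reaction combined (modestly, 1.1–1.7 times the low sum) or per-unit analysis with repeat dosing (up to 7.8 times, for circulatory overload). Such a result would speak only to the higher figure.

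These figures assume one observation per recipient except where units are named, one infusion equal to one unit, and independence between units. The mean number of doses is not given; the possible range is 150 to 600 infusions. With more units the limits tighten: zero events in 600 gives an upper limit of 1 − 0.025^(1/600) = 0.61%, below the circulatory-overload and febrile figures but still above the lung-injury figure. This is why the unit of analysis has to be settled.

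**What to change.** In item 2 of the Statistical Plan:

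1. Replace the chi-square with the count and Clopper-Pearson 95% confidence interval for each reaction and for any reaction, beside both ends of the published range. The plan has no any-reaction rate, so if the four are summed, say so and state the non-overlap assumption.
2. Test for excess with an exact binomial test against the prespecified higher figure, and state its direction and level. Keep the low-end comparison descriptive.
3. State the unit of analysis, patient or plasma unit, so that it matches the reference rate. Say how repeat doses in one patient are handled, and whether 1+ versus 0 is scored per type or for any reaction.
4. Allow no-excess wording only when the upper confidence limit is below the stated figure. Draw no safety conclusion from a lower result.

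The cost is wording and a few exact intervals, with no new data. The exact test corrects the lung-injury false alarm but does not lower the circulatory-overload threshold: at a one-sided 5% level it is still 6/150 or 7/200. The real downside is that for the rarer reactions the study will have to report that it cannot rule out an excess.

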38 1) Change in clinical status as captured by 7-point ordinal scale score (being utilized in Gilead Sciences
39 remdesivir trial^{19, 20}) at time of plasma infusion (day 0) compared to day 7:

40

- 44 1. Death
- 45 2. Hospitalized, requiring mechanical ventilation or ECMO

- 1 3. Hospitalized, requiring non-invasive ventilation or high flow oxygen
- 2 4. Hospitalized, requiring supplemental oxygen
- 3 5. Hospitalized, not requiring supplemental oxygen--requiring ongoing medical care
- 4 (COVID-19 related or otherwise)
- 5 6. Hospitalized, not requiring supplemental oxygen-not requiring ongoing medical care
- 6 (COVID-19 related or otherwise).
- 7 7. Not Hospitalized

8 2) Adverse events related to plasma infusion (within 6 hours of infusion) to include²³:

- 9 a) Transfusion-related events
 - 10 i. Transfusion Associated Circulatory Overload
 - 11 ii. Transfusion-Related Lung Injury
 - 12 iii. Allergic Reaction/Anaphylaxis
 - 13 iv. Transmission of transfusion transmitted diseases
 - 14 v. Febrile Transfusion Non-hemolytic Transfusion Reaction

15 Secondary Endpoints:

- 16 3) Change in 7-point ordinal scale score (being utilized in Gilead Sciences remdesivir trial) from time
- 17 of plasma infusion (day 0-prior to first infusion) to days 14, 21, and 28^{19,20}.
- 18 4) SOFA score at days 0, 7, 14, 21, 28²¹
- 19 5) Time to discontinuation of supplemental oxygen
- 20 6) Duration of hospitalization
- 21 7) Time to liberation from mechanical ventilation (for patients on a ventilator)
- 22 8) Need for mechanical ventilation (For those not on the ventilator)
- 23 9) All-cause Mortality [at 28 days]

24 ○

| Organ System, Measurement | SOFA Score | | | | |
|--|------------|-------------------|--|--|---|
| | 0 | 1 | 2 | 3 | 4 |
| Respiration PaO ₂ /FiO ₂ , mmHg | Normal | <400 | <300 | <200 (with respiratory support) | <100 (with respiratory support) |
| Coagulation Platelets x10 ³ /mm ³ | Normal | <150 | <100 | <50 | <20 |
| Liver Bilirubin, mg/dL (μmol/l) | Normal | 1.2-1.9 (20-32) | 2.0-5.9 (33-101) | 6.0-11.9 (102-204) | >12.0 (<204) |
| Cardiovascular Hypotension | Normal | MAP<70 mmHg | Dopamine ≤5 or dobutamine (any dose)** | Dopamine >5 or epinephrine ≤0.1 or norepinephrine ≤0.1 | Dopamine >15 or epinephrine >0.1 or norepinephrine >0.1 |
| Central Nervous System Glasgow Coma Score | Normal | 13-14 | 10-12 | 6-9 | <6 |

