25 appropriate. Treating physician will notify the study doctor and staff if there is an adverse reaction.

26 Possible anticipated infusion related reactions could include:

27 1) Transfusion Associated Circulatory Overload – dose of intravenous furosemide may be
28 considered
29 2) Transfusion-Related Lung Injury- supportive care as directed by treating physician
30 3) Allergic Reaction/Anaphylaxis – additional dose of diphenhydramine, dose of intravenous or oral
31 corticosteroids or intramuscular epinephrine could be considered
32 4) Transmission of transfusion transmitted diseases – supportive care or targeted treatment if
33 infection identified
34 5) Febrile Transfusion Non-hemolytic Transfusion Reaction – supportive care

35 These adverse events, if present, will be recorded by clinical research team.

36

37 **Post-Treatment Blood Draws:**

38 Optional blood draws (up to four tubes) may be drawn on days 7, 14, 21, and 28 (+/2 days) following each
39 dose of convalescent plasma where feasible for Biobanking.

40 If patient is discharged prior to 7 days post-dosing, then follow-up phone call or email assessments
41 will be made by study staff at 7 days, 14 days, 21, and 28 days (+/2 days) following the original dose.

1
2 **Script for Phone Call(s) or Email(s) to Recipients (if applicable):**

3 1) Are you in a home environment (your home or family member's home)?
4 2) If not, are you in a nursing or rehabilitation facility?
5 3) Are you using oxygen?
6 4) Have you required an urgent care or emergency room visit for any reason since your
7 discharge?
8 5) Have you required re-hospitalization for any reason since your discharge?

9
10 **Trial Methods**

11 Convalescent plasma will be made available to patients hospitalized in the Inova Heath System.

12
13 Patient outcome monitoring and reporting will include indicators of safety and efficacy. Case Report
14 Forms will be used to capture essential data.

15
16 **Statistical Plan**

17 Study parameters (e.g., clinical status scale, death, hospitalization, etc.) will be described using traditional
18 descriptive statistics (median [IQR], frequency and percent). Data will be assessed for 'missingness' with
19 parameters exceeding 10% missing explored for imputation (e.g., multiple imputation, last value carried
20 forward, etc.). Departures from normality will be assessed via Shapiro-Wilkes test with data

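### The planned SOFA growth model omits day 7, a day at which the SOFA endpoint is defined; SOFA needs its own list of times and a stated non-linear form for time

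*Combined protocol and SAP*

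**What the plan says.** All references are to the combined protocol and SAP.

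- **Secondary Endpoints, item 4** lists the SOFA score at five times: days 0, 7, 14, 21 and 28.
- **Secondary Endpoints, item 3** covers change on the 7-point ordinal scale from the time "of plasma infusion (day 0-prior to first infusion) to days 14, 21, and 28". Day 7 is absent because the day 0 to day 7 change on that scale is the primary endpoint.
- **Statistical Plan, Secondary endpoints, item 1** handles both outcomes together: "Change in 7-point ordinal scale score and SOFA score over time will be assessed via individual" "growth models (IGM). Times will be day0, 14, 21, and 28". No other analysis item names SOFA, and no form for time is given.
- **Statistical Plan, opening paragraph** has a general descriptive statement, "Study parameters (e.g., clinical status scale, death, hospitalization, etc.) will be described using traditional" statistics, and a general missing-data statement, "parameters exceeding 10% missing explored for imputation (e.g., multiple imputation, last value carried" forward. Neither mentions SOFA, a visit day or death.
- **Script for Phone Call(s) or Email(s) to Recipients** asks discharged patients about where they are living, oxygen use ("Are you using oxygen") and later urgent-care, emergency or hospital visits. It collects no SOFA component.
- **Statistical Plan, Secondary endpoints, item 4** says that time to oxygen discontinuation, time to ventilator liberation and "duration of hospitalization will be summarized as median (IQR) or rates and compared to currently" published estimates. It does not say how deaths are counted.

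**The concern.** One list of times has been applied to two outcomes and is right for only one of them. For the ordinal scale, leaving day 7 out of the secondary model is coherent, since day 7 is tested as primary. SOFA has no separate day-7 analysis, so its day-7 score is defined as an endpoint and then left out of the only model planned for it.

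What is at stake is whose change the model describes. Patients may be discharged once a 24-hour observation period after infusion is complete, and SOFA cannot be obtained from the follow-up calls. A patient who leaves or dies between days 7 and 14 can have an observed change from day 0 to day 7, but on the planned list supplies a baseline score only. Observed change then comes from patients with a score at day 14 or later, in the main those still in hospital, and the first week is not modelled.

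A smaller, related gap is that the ordinal scale scores death as category 1 while the SOFA table has no value for death. The missing-data sentence does not rule out carrying a SOFA score forward after death.

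**Working it through.** **Step 1. Compare the lists.** The plan states no SOFA figure to reproduce, so the first check is a comparison of days.

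| | Day 0 | 7 | 14 | 21 | 28 |
|---|---|---|---|---|---|
| SOFA endpoint (item 4) | yes | yes | yes | yes | yes |
| Secondary ordinal endpoint (item 3) | yes | no | yes | yes | yes |
| Growth model, both outcomes | yes | **no** | yes | yes | yes |

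The model list equals the ordinal list. It differs from the SOFA list by day 7 alone.

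**Step 2. How many patients could be affected.** The documents give the recipient target (150-200) but no length-of-stay distribution, so the rest is assumed. Let p be the share dying, d the median day of death, m the median day of discharge, and F(t; median) the lognormal distribution function with log-scale standard deviation σ. The share who have died or left by day t is

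A(t) = p·F(t; d) + (1 − p)·F(t; m).

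The share with a day-7 score but none from day 14 on is A(14) − A(7). I take p = 0.05, the top of the 1-5% mortality rate hypothesized in the plan, with d = 9, m = 10-20 and σ = 0.4-1.0.

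Example, m = 14 and σ = 0.6:
- A(14) = 0.05 × 0.769 + 0.95 × 0.500 = 0.513
- A(7) = 0.05 × 0.338 + 0.95 × 0.124 = 0.135
- Difference = 0.379 from unrounded values

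| σ | m = 10 | m = 14 | m = 20 |
|---|---|---|---|
| 0.4 | 0.613 | 0.466 | 0.203 |
| 0.6 | 0.436 | 0.379 | 0.246 |
| 0.8 | 0.335 | 0.308 | 0.238 |
| 1.0 | 0.271 | 0.257 | 0.217 |

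The range is 20-61%, or 30-92 of 150 and 41-123 of 200. The baseline-only share is 22-80% on the planned list and 2-36% with day 7 included.

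Sensitivity:
- Deaths 1-5% and death median 9-18 days: 18-61%.
- Weibull times (shape 1-2) over the same death ranges: 17-46%.
- Outside m = 10-20 the share can be smaller: at σ = 0.4, p = 0.05 and d = 9 it is 11% for m = 4 and 6% for m = 30.

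**Step 3. Precision.** For a straight line with complete data, slope variance is proportional to 1/S, where S is the sum of squared deviations of the times from their mean.
- Days 0, 14, 21, 28 (mean 15.75): S = 428.75
- Days 0, 7, 14, 21, 28 (mean 14): S = 490
- Standard error ratio = √(428.75/490) = 0.935, a reduction of 6.5%

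This is a ceiling. Any between-patient variation in slope adds a term that day 7 does not reduce.

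**Step 4. Does adding day 7 to a straight line help?** Two assumed SOFA paths, expressed as change from day 0. The fitted 28-day change is 28 × Σ(t − mean)·y / S.

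| Path | True day-28 change | Line without day 7 | Line with day 7 |
|---|---|---|---|
| Falls 4 by day 7, then flat | −4 | 28 × (−63/428.75) = −4.11 | 28 × (−56/490) = −3.20 |
| Rises 2 at day 7, then 2 below baseline from day 14 | −2 | 28 × (−31.5/428.75) = −2.06 | 28 × (−56/490) = −3.20 |

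In both, adding day 7 to a straight line moves the fitted change away from the truth. Categorical time returns the true value at each visit. A two-piece line with a knot at day 7 recovers the first path exactly. For the second path its fitted values are 0, 0.8, −0.4, −1.6 and −2.8, so the day-28 error shrinks from 1.2 to 0.8 but remains.

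**The case against.** - **Day-7 SOFA can still be reported.** The endpoint is the score at each day, and the general descriptive sentence has an open list. This stands: a reader might infer that day-7 SOFA is lost from the trial altogether, and the documents do not support that. A descriptive summary does not, however, put day 7 into the model.
- **Imputation could bring day 7 back in.** In the lognormal scenarios of Step 2 with median stay 10-20 days, at least 22% of patients have no score at day 14. That exceeds the 10% threshold, so imputation would be explored, and either method named could use a day-7 score. Readmitted patients might also have later scores. This partly stands. It is wrong to say that these patients must enter with a baseline score only, but the plan commits to no method, and an imputed change is not an observed one.
- **The patient counts rest on assumed stays.** This stands. The 20-61% is neither an estimate nor a bound, and it counts patients. A reader might take it for a bias in the SOFA result; no such bias is shown.
- **The precision gain is small.** This stands. The 6.5% requires complete data, which early discharge rules out, and no between-patient slope variance.
- **Adding day 7 alone can make the estimate worse.** This stands for a straight line (Step 4), so the correction must state the form for time.
- **The death-handling points are mostly missing detail.** This stands. The 1-5% is a hypothesized reference rate for a test, not a forecast for these severe or life-threatening cases. On the assumptions tried at that mortality, counting deaths differently moves median stay by at most about 2 days.

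**Conclusion.** The inconsistency is real and needs no assumption: the SOFA endpoint includes day 7 and the only SOFA model excludes it, on a list that fits the ordinal scale alone. As written, the model sets aside a defined score, and patients who die or leave between days 7 and 14 add no observed SOFA change. How many that is cannot be known from the documents. About one in five to three in five is plausible under the assumed median stays of 10-20 days, and fewer if stays are much shorter or longer.

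The documents do not support the stronger inferences that the SOFA result is biased by a known amount, that precision suffers materially, or that the trial's main conclusion is at risk. This is a secondary analysis in a single-arm study, and the primary day 0 to day 7 ordinal comparison is untouched. It should be corrected because the text is wrong as it stands and the correction is cheap. How deaths are counted in the duration outcomes is a minor clarification and does not carry the point.

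**What to change.** In the Statistical Plan, Secondary endpoints, item 1:

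1. Give SOFA its own times, days 0, 7, 14, 21 and 28. Leave the ordinal-scale list as it is.
2. State the form for time in the SOFA model: categorical, or piecewise (for example with a knot at day 7). Report the change from day 0 at each visit. Categorical time is the safer choice, since a knot at day 7 does not capture every path (Step 4).
3. State that SOFA is not imputed or carried forward after death.
4. Report the numbers dead and discharged at each SOFA visit, so that the reader can see who supplies each estimate.

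As a minor clarification, state in item 4 how deaths are counted in each duration outcome.

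The cost is a few sentences in the plan, a few extra model parameters and slightly more analysis work, all within standard SAS procedures. No new visits, calls or data are needed.

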1
2
3
4
5
6
7
8
9
10
11
12
13
14
15
16
17
18
19
20
21
22
23
24
25
26
27
28
29
30
31
32
33
34
35
36
37
38
39
40
41
42
43
44
45
46 **Study Proposal**

1
2 **Study Title: Open-label Treatment of severe Coronavirus Disease 2019 (COVID-19) with**
3 **convalescent plasma collected from individuals with documented infection and recovery from**
4 **COVID-19 (SARS-CoV-2)**

5
6 **Investigators:**

7 **Principal Investigator:**
8 A. [name]
9 [name]

10
11 **Co-Investigators:**

12 [name], NP
13 [name], NP
14 [name], PA
15 [name], NP
16 [name]
17 [name]
18 [name]
19 [name]
20 [name]
21 [name]
22 [name]
23 [name]
24 [name]
25 [name]
26 [name]
27 [name]
28 [name]
29 [name]
30 [name], BS MLS (ASCP)H, HP

31
32
33
34
35 **Name/Address of Institution:**

36 Inova Health System
37 Inova Fairfax Hospital
38 [name]
39 [name]

1 **Study Hypothesis:**

2 We hypothesize that use of convalescent plasma donated from individuals recovered from Coronavirus
3 Disease 2019 (COVID-19) will help expedite recovery of individuals with active, severe COVID-19
4 infection.

5
6 **Study Background:**

7 Plasma obtained from convalesced (recovered from virus) individuals may be an effective treatment or
8 prevention of viral disease through the transfer of passive immunity in the form of neutralizing
9 antibodies¹.

10 Convalescent plasma therapy can be considered as a candidate intervention in the setting of an expanding
11 viral epidemic of public health concern for which vaccines and approved antiviral drugs are unavailable².
12 It has been used to treat patients with Machupo virus (Bolivian hemorrhagic fever), Junin virus
13 (Argentinian hemorrhagic fever), Lassa fever, and most recently, Ebola virus, West Nile encephalitis,
14 SARS and Middle East respiratory syndrome (MERS)³⁻⁸. During the 2009 H1N1 (H1N1pdm09) virus
15 epidemic, a prospective cohort study by Hung and colleagues showed a significant reduction in the
16 relative risk of mortality (odds ratio 0·20 [95% CI 0·06–0·69], p=0·01) for patients treated with
17 convalescent plasma⁵. During the Ebola epidemic in West Africa, investigational use of convalescent
18 plasma demonstrated that it can be successfully collected from donors with recent infection, and used
19 safely and effectively for treatment in affected individuals⁷. In 2014, World Health Organization (WHO)

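### The growth model for the ordinal and SOFA secondary endpoints has no stated time form or contrast; a straight-line form would not estimate the day-specific changes the ordinal endpoint names

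*Combined protocol and SAP*

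**What the plan says.** Under Secondary Endpoints, item 3 is the change in the 7-point score from the time "of plasma infusion (day 0-prior to first infusion) to days 14, 21, and 28". These are three changes, each tied to a day. Item 4 is SOFA, listed as a score at days 0, 7, 14, 21 and 28 and not worded as a change.

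Under Statistical Plan, Secondary endpoints, item 1, one analysis covers both: "Change in 7-point ordinal scale score and SOFA score over time will be assessed via individual" "growth models (IGM). Times will be day0, 14, 21, and 28". Nothing further is said about whether time is linear, curved or categorical, which random effects are used, or which quantity is reported. Day 7 is not among the model times, although the SOFA endpoint includes it.

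The scale is bounded: 1 is death and the top category is "7. Not Hospitalized". The Study Hypothesis is that plasma "will help expedite recovery of individuals with active, severe COVID-19" infection. The recipient target is "150-200 individuals".

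**The concern.** A growth model describes a trajectory. In its simplest form it reduces each patient to a starting level and a rate. The ordinal endpoint asks for something else: how far patients have moved by three particular days. The plan does not say how those three changes would be read off the model.

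The scale makes the gap matter. A patient who goes home or dies moves in one step and can then stay at 7 or 1. A straight line through a step and a plateau tends to miss the change at the individual days. Because the hypothesis concerns faster recovery, it is also awkward if the reported rate can be lower for patients who recover sooner. What is at stake is the size of the reported secondary effects, and the SOFA day-7 result, which has no place in the stated analysis.

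**Working it through.** The plan gives no slope, effect size or power for this analysis, so there is no figure of its own to reproduce. The check takes the planned days (0, 14, 21, 28) and assumes linear time, which the plan does not state.

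**Slope weights.** Mean day = 63/4 = 15.75. Sum of squared deviations = 248.0625 + 3.0625 + 27.5625 + 150.0625 = 428.75. The least-squares slope is Σ(t − 15.75)y / 428.75, so the weights are −15.75, −1.75, +5.25 and +12.25, each over 428.75. With complete balanced data and independent residuals, a random-intercept and random-slope model has the same fixed slope. The day-14 weight is negative: with the other scores held fixed, a better day-14 score lowers the slope.

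**Step courses.** Assume a patient starts at 3, moves to 7 in one step and stays there. The implied change at a day is the slope times that day.

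| Scores at days 0, 14, 21, 28 | Slope per day | Implied change at 14 / 21 / 28 | Actual change |
|---|---|---|---|
| 3, 7, 7, 7 | 63/428.75 = 0.147 | 2.06 / 3.09 / 4.11 | 4 / 4 / 4 |
| 3, 3, 7, 7 | 70/428.75 = 0.163 | 2.29 / 3.43 / 4.57 | 0 / 4 / 4 |
| 3, 3, 3, 7 | 49/428.75 = 0.114 | 1.60 / 2.40 / 3.20 | 0 / 0 / 4 |

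Recovery by day 14 is 10% below recovery by day 21 (63/70 = 0.90) and 29% above recovery seen only by day 28 (63/49 = 1.29). These ratios do not depend on the size of the gain.

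**Sensitivity of the ranking.**
- AR(1) residuals with 7-day correlation 0.5, 0.8 or 0.95 keep the order day 21, day 14, day 28. Per point gained, the day-14 and day-21 slopes are 0.03584 and 0.03828, 0.03572 and 0.03629, and 0.03571 and 0.03576. The day-21 advantage is thus about 7%, 2% and 0.1%.
- A line forced through the baseline score has slope Σt·(change)/Σt², with Σt² = 196 + 441 + 784 = 1,421. A 4-point gain gives 252/1,421 = 0.177, 196/1,421 = 0.138 and 112/1,421 = 0.079 for recovery by days 14, 21 and 28. The order is then the natural one.
- With day 7 added and a free intercept (sum of squares 490), recovery by days 7, 14, 21 and 28 gives 56/490, 84/490, 84/490 and 56/490, that is 0.114, 0.171, 0.171 and 0.114.

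**Day-specific changes for a cohort.** Assume, for illustration only, mean scores of 3.15, 4.51, 4.84 and 5.05. The actual changes are 1.36, 1.69 and 1.90.
- Free intercept: slope = (−49.61 − 7.89 + 25.41 + 61.86)/428.75 = 0.0694. Day 14 = 0.97 (29% too small); day 28 = 1.94.
- AR(1) residuals, same correlations: day 14 = 0.95 to 0.96.
- Anchored at baseline: slope = (19.04 + 35.49 + 53.20)/1,421 = 0.0758. Day 14 = 1.06 (22% too small); day 28 = 2.12 (12% too large).
- Quadratic: the one contrast left unfitted has weights −1, 6, −8, 3, value 0.34 and sum of squares 110. Residuals are those weights times 0.34/110, or −0.003 at day 0 and +0.019 at day 14. Day 14 = (4.51 − 0.019) − (3.15 + 0.003) = 1.34, close to 1.36.

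**Categorical time.** On complete data this returns 1.36, 1.69 and 1.90 exactly. For the step courses it returns the last column of the table, where earlier sustained recovery is never scored below later recovery.

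**The case against.** The strongest reply is that the plan never says linear and never names a slope as the reported effect. A curved growth model is allowed by the same words, and on the assumed means a quadratic nearly removes the day-14 error. This stands: every size above is conditional on a straight line. It also shows that the result turns on a choice the plan leaves open.

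A reader might infer that the planned analysis rewards slower recovery in general. The documents do not support that. Even with a straight line and a free intercept, recovery seen only by day 28 gets the smallest slope. The gap between days 14 and 21 shrinks under serial correlation, and anchoring at baseline reverses it. Nor is there a comparator group whose slope could be favoured, and every recovery course shown has a positive slope.

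A reader might also take both endpoints to be changes at days 14, 21 and 28. Only the ordinal one is. The step-and-plateau argument is made for the ordinal scale; for SOFA, the visible fault is the missing day 7.

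Three further points are fair. The documents do not say how many patients plateau, and the recipient follow-up script asks about re-hospitalization, so 7 need not be final. Speed of recovery is also addressed by the day-7 primary endpoint, the time to stopping oxygen, the time to ventilator liberation and the duration of hospitalization. And the Statistical Plan already provides for frequencies and percents of the clinical status scale. These points limit the consequence; they do not supply the missing contrast.

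**Conclusion.** The concern holds in a limited form. The ordinal endpoint is three day-specific changes, and the named analysis is a growth model with no stated time form or contrast. If time is linear, the slope does not estimate those changes: on the assumed means, day 14 comes out at 0.97 (free intercept) or 1.06 (anchored) against 1.36. With a free intercept it also ranks recovery by day 14 (0.147/day) below recovery by day 21 (0.163/day), though above recovery seen only by day 28 (0.114/day). A curved form may reduce this. The omission of day 7 for SOFA is an inconsistency whatever the form.

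The sizes rest on linear time, a single sustained 4-point step and illustrative cohort means, none of which the documents give. These are secondary endpoints, so the primary day-7 analysis is not touched. The change is still worth making, because a method that targets the stated ordinal endpoint directly is available from the same data.

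**What to change.** In Statistical Plan, Secondary endpoints, item 1, replace the growth model with a repeated-measures model that has time as a categorical factor and allows for within-patient covariance. Report each scheduled day against day 0 with a 95% confidence interval: days 14, 21 and 28 for the ordinal score, and days 7, 14, 21 and 28 for SOFA. Beside the ordinal estimates, show the number and percent in each of the seven categories at each day, which the plan's descriptive statistics already cover. If a growth curve is kept, state its form and label it supportive.

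The cost is a change of wording and some extra parameters. With unstructured covariance at four times there are 10 covariance parameters, against 4 for random intercept, random slope, their covariance and the residual. Mean parameters rise from 2 to 4, so the total rises by 8. For SOFA at five times the counts are 15 and 5, a rise of 14. With 150 to 200 recipients this is small. The model still treats the ordinal categories as equally spaced numbers, which is why the category counts should sit beside it.
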